### 8.0 RISKS/PRECAUTIONS

Refer to the ASTX727 IB for the most current risks and precautions, as well as a list of AEs considered expected with ASTX727 therapy. As with any IMP, subjects may experience reactions or complications that are unknown and are therefore unpredictable.

# 8.1 Drug-Drug Interactions

The primary activity of cedazuridine is the inhibition of CDA, which enhances the bioavailability of orally administered decitabine. Therefore, drugs known to be metabolized by CDAs should not be given (such drugs include cytarabine, gemcitabine, azacytidine, vidarabine, zalcitabine, zidovudine, telbivudine, didanosine, zalcitabine, stavudine, lamivudine, abacavir, emtricitabine, entecavir, apricitabine, idoxuridine, trifluridine, tenofovir and adefovir) on days when ASTX727 is administered and for 24 hours thereafter. As new agents may come to market during the trial, confer with the medical monitor if questions arise.

ASTX727 is not expected to produce cytochrome P450 (CYP)-mediated drug-drug interaction, as ASTX727 has shown no potential to inhibit or induce human CYP enzymes in vitro.

# 8.2 Genotoxicity

ASTX727 is shown to be genotoxic, which could cause fetal harm. Therefore, subjects with reproductive potential must use methods of contraception during the study (as described in Section 5.0) and for 3 months after the last dose of study treatment. Subjects should promptly notify the investigator if they, or their partner, become pregnant during this period. If a female subject becomes pregnant during the treatment period, she must discontinue study treatment immediately (see Section 10.2.3).

### **8.3** Overdose Instructions

Record the actual dose of study treatment administered in the source document and on the Dosing eCRF. Record any adverse clinical signs and symptoms associated with a potential overdose on

the AE eCRFs. Report signs and symptoms of a potential overdose that meet SAE criteria (defined in Section 10.1.2) on the SAE form within 24 hours (see Section 10.3). Treat any AE (including SAEs) based on standard care for the specific signs and symptoms.

No data are available regarding overdosage of ASTX727. Based on the clinical experience of decitabine, an overdosage of ASTX727 may result in more profound or prolonged myelosuppression and its consequences such as infection, or bleeding, or GI toxicity, and subjects should be managed accordingly. No antidote has yet been developed for overdose of ASTX727.

### 9.0 STUDY ASSESSMENTS AND PROCEDURES

### 9.1 Pharmacokinetics

The schedules for PK assessments during the ASTX727 and IV decitabine cycles are provided in Table 6 and Table 7, respectively. Pharmacokinetics will be evaluated on Days 1 through 5 during the cycle of ASTX727 administration (serial collections on Days 1, 2, and 5, trough levels on Days 1-5, and once on Day 3), and on Days 1, 3, and 5 during the cycle of IV decitabine administration. Adequate PK assessments in both Cycles 1 and 2 (see Section 11.2.2) will be required for subjects to be evaluable for the primary study endpoint.

During the IV decitabine cycle, the contralateral arm should be used for PK blood draws. No blood draws for PK assessments should be done from the arm used for IV decitabine infusion.

Detailed instructions for PK sample collection will be provided separately from the protocol. The total blood volume planned for Cycle  $1 + \text{Cycle } 2 = \sim 171 \text{ mL}$ . The blood draw schedule may be modified by Astex.

Table 6: Schedule of Pharmacokinetics Assessments – ASTX727 Cycle

|   |    |    | ASTX | 727 Cycl | e |      |
|---|----|----|------|----------|---|------|
| Cycle Day                                     | 1  | 2  | 3    | 4        | 5 | 6-28 |
| Pre-dose (within 90 min before dosing) | ×  | ×a | ×a,b | ×        | × |      |
| TIME AFTER ORAL DOSE                          |    |    |      |          |   |      |
| 15 min (± 2 min)                       | ×  | ×  |      |          | × |      |
| 30 min (± 2 min)                       | ×  | ×  |      |          | × |      |
| 1 hour (± 3 min)                       | ×  | ×  |      |          | × |      |
| 1.5 hours (± 3 min)                    | ×  | ×  |      |          | × |      |
| 2 hours (± 3 min)                      | ×  | ×  |      |          | × |      |
| 3 hours (± 5 min)                      | ×  | ×  | ×b   |          | × |      |
| 4 hours (± 5 min)                      | ×  | ×  |      |          | × |      |
| 6 hours (± 10 min)                            | ×  | ×  |      |          | × |      |
| 8 hours (± 10 min)                            | ×  | ×  |      |          | × |      |
| 24 hours (± 60 min) a              | ×a | ×a |      |          |   |      |

The pre-dose time point is the same as the 24-hour time point on the previous day; the 24-hour time point is the same as the pre-dose time point on the following day.

NOTE: Volume per blood draw = 3 mL. Total blood volume planned for the ASTX727 cycle =  $\sim$ 99 mL.

NOTE: Every effort should be made to collect PK samples within the specified sampling windows.

Table 7: Schedule of Pharmacokinetics Assessments – IV Decitabine Cycle

|  |                                     |    |    | IV De | citabi | ne Cycle |  |
|--|-------------------------------------|----|----|-------|--------|----------|--|
|  | 1                                   | 2  | 3  | 4     | 5      | 6-28     |  |
| Pre-dose (within 90 min before         | ×                                   |    | ×b |       | ×      |          |  |
| TIME AFTER START OF                    | TIME AFTER END OF                   |    |    |       |        |          |  |
| INFUSION                               | INFUSION                            |    |    |       |        |          |  |
| 15 min (± 2 min)                |                                     | ×  |    |       |        | ×        |  |
| 30 min (± 2 min)                |                                     | ×  |    |       |        | ×        |  |
| 1 hour $(59 \min \pm 1 \min)^a$ |                                     | ×a |    | ×b    |        | ×a       |  |
| 1 hour 5 min (± 1 min)                 | 5 min (± 1 min) c | ×  |    |       |        | ×        |  |
| 1.5 hours (± 3 min)                    | 30 min (± 3 min)             | ×  |    |       |        | ×        |  |
| 2 hours (± 3 min)                      | 1 hour (± 3 min)             | ×  |    |       |        | ×        |  |
| 3 hours (± 5 min)                      | 2 hours (± 5 min)            | ×  |    |       |        | ×        |  |
| 4 hours (± 5 min)                      | 3 hours (± 5 min)            | ×  |    |       |        | ×        |  |
| 6 hours (± 10 min)                     | 5 hours (± 10 min)           | ×  |    |       |        | ×        |  |
| 8 hours (± 10 min)                     | 7 hours (± 10 min)           | ×  |    |       |        | ×        |  |

<sup>a Obtain the 1-hour PK sample immediately prior to the end of infusion (59 min  $\pm$  1 min).

NOTE: Blood draws for PK should be made from the contralateral arm (arm not used for IV infusion). Volume per blood draw = 3 mL. Total blood volume planned for the IV decitabine cycle =  $\sim 72 \text{ mL}$ .

NOTE: Every effort should be made to collect PK samples within the specified sampling windows.

b Time-matched PK assessment for QTc on Day 3: ECG is to be done predose and at 3 hr ± 5 min. PK blood draw should be done immediately after completion of ECG for QTc.

b Time-matched PK assessment for QTc on Day 3: ECG is to be done predose and within 10 min before end of infusion. PK blood draw should be done immediately after completion of ECG for QTc but before the end of the infusion.

<sup>c The clock for 5 min post-infusion should begin when the infusion is finished.

### 9.2 Efficacy Assessments

The response criteria for evaluation of MDS are based on the International Working Group (IWG) criteria published by Cheson et al (2006) modified as shown in Table 8.

Complete response (CR), marrow CR (mCR), partial response (PR), and hematologic improvement (HI) will be determined based on peripheral blood counts and bone marrow aspirate/biopsy at the scheduled assessment days. Red blood cell (RBC) or platelet TI for at least 56 consecutive days will be determined in subjects who are transfusion dependent at baseline of study ASTX727-02. Leukemia free survival is defined as the number of days from the date of randomization to the date when bone marrow or peripheral blood blasts reach ≥20%, or the date of death from any cause. Overall survival is determined from the date of randomization to the date of death from any cause.

# Table 8: Response Categories Based on IWG 2006 MDS Response Criteria

### Complete Response (CR): the following for at least 4 weeks

**Peripheral:** normal peripheral counts with persistent granulocyte count  $\ge 1.0 \times 10^9$ /L, platelet  $\ge 100 \times 10^9$ /L, and Hgb  $\ge 11 \text{ g/dL}$ .

Marrow: normal bone marrow with persistent marrow blasts ≤5%; persistent dysplasia will be noted.

### Partial Response (PR): the following for at least 4 weeks

**Peripheral:** normal peripheral counts with granulocyte count  $\ge 1.0 \times 10^9$ /L, platelet count  $\ge 100 \times 10^9$ /L, and Hgb  $\ge 11$ g/dL.

Marrow: normal bone marrow and marrow blasts >5% but were reduced by 50% or more.

### Marrow Complete Response (mCR): the following at least for 4 weeks

Reduction of bone marrow blasts to ≤5% and decrease by 50% or more with or without normalization of peripheral counts

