### 5.2 Inclusion Criteria

To be eligible for the study, subjects must fulfill all of the following inclusion criteria:

- 1) Able to understand and comply with the study procedures, understand the risks involved in the study, and provide legally effective informed consent before the first study-specific procedure; specifically able to comply with the PK assessment schedule during the first 2 treatment cycles.
- 2) Men or women ≥18 years who are candidates to receive IV decitabine, ie, subjects with MDS previously treated or untreated, with de novo or secondary MDS, including all French-American-British subtypes (refractory anemia, refractory anemia with ringed sideroblasts, refractory anemia with excess blasts, refractory anemia with excess blasts in transformation, and CMML), and subjects with MDS IPSS int-1, -2, or high-risk MDS.
- 3) ECOG performance status of 0 to 1.
- 4) Adequate organ function defined as follows:
  - a) Hepatic: Total or direct bilirubin  $\leq$ 2 × upper limit of normal (ULN); AST/SGOT and ALT/SGPT  $\leq$ 2.5 × ULN.
  - b) Renal: serum creatinine ≤1.5 × ULN or calculated creatinine clearance or glomerular filtration rate >50 mL/min/1.73 m² for subjects with creatinine levels above institutional normal.
- 5) No major surgery within 30 days of first study treatment.
- 6) Life expectancy of at least 3 months.

- 7) Women of child-bearing potential must not be pregnant or breastfeeding and must have a negative pregnancy test at screening. Women of non-childbearing potential are those who have had a hysterectomy or bilateral oophorectomy, or who have completed menopause, defined as no menses for at least 1 year AND either age ≥65 years or follicle-stimulating hormone levels in the menopausal range.
- 8) Subjects and their partners with reproductive potential must agree to use effective contraceptive measures during the study and for 3 months after the last dose of study treatment. Effective contraception includes methods such as oral contraceptives or double-barrier method (eg, use of a condom AND diaphragm, with spermicide).

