- Bone marrow aspirate or biopsy: At Screening or within 21 days before Cycle 1 Day 1; on or before Day 1 of Cycles 3, 5, 7, and then every 3 months in first year and every 6 months thereafter. Bone marrow aspirate or biopsy differential will be performed according to local standard practice. A bone marrow biopsy can be done if no aspirate is available. A manual differential of the myeloid cells in bone marrow will be performed with a minimum of 100 cells counted and a specific myeloblast percent generated. Bone marrow aspirate or biopsy differential may include the following: total cells counted, metamyelocytes, lymphocytes, normoblasts, myeloid and erythroid maturation, blasts, segmented neutrophils, plasma cells, megakaryocytes, presence of dysplasia, promyelocytes, eosinophils, monocytes, M:E ratio, cellularity: % cellularity; hypocellular, hypercellular, normocellular; myelocytes, basophils, pronormoblasts, and other. An anonymized report of all bone marrow testing results will be recorded on the electronic Case Report Form. A portion of bone marrow aspirates will be used for assessing disease-associated gene mutations. Cytogenetics will be reviewed on the screening bone marrow and should include at least 20 clones. If cytogenetics are abnormal, they must be reviewed again in subsequent bone marrow aspirates or biopsies.

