## 11.7.1 Clinical Response

Complete response, mCR, PR, and HI (also HI-E, HI-P, and HI-N separately) will be summarized for all subjects in the Efficacy Analysis Set. The rate of each response status and its 95% Wald CIs will be provided, respectively.

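### The marrow CR rule states no baseline blast percentage above 5%, so eligible low-blast subjects can count as responders on a change of one or two cells held for 4 weeks

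*Protocol*

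**What the plan says.** Protocol Section 9.2, Table 8, heads the row "Marrow Complete Response (mCR): the following at least for 4 weeks" and defines the response as "Reduction of bone marrow blasts to ≤5% and decrease by 50% or more with or without normalization of peripheral counts". The row therefore has three conditions: blasts at or below 5%, a fall of at least half, and 4 weeks' duration. It requires no blood-count recovery and states no starting value. The Table 8 footnote on baseline concerns peripheral counts and transfusions, not marrow blasts.

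Section 5.2, criterion 2, admits MDS "including all French-American-British subtypes (refractory anemia, refractory anemia with ringed sideroblasts" among them, and "subjects with MDS IPSS int-1, -2, or high-risk MDS". No inclusion or exclusion criterion sets a marrow blast minimum.

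The marrow footnote to Table 9 asks for a manual differential "performed with a minimum of 100 cells counted and a specific myeloblast percent generated", with marrows at screening and "on or before Day 1 of Cycles 3, 5, 7, and then every 3 months in first year". Section 11.7.1 says: "Complete response, mCR, PR, and HI (also HI-E, HI-P, and HI-N separately) will be summarized for all subjects in the Efficacy Analysis Set".

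The supplied SAP covers AML subjects only. Its Section 1.0 says that MDS/CMML subjects have a separate SAP, which is not among the documents available here.

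**The concern.** A subject whose screening marrow shows 5% blasts or fewer has no excess blasts to clear. The mCR row still lets that subject respond if the blast percentage halves and stays halved for 4 weeks. At these levels, halving means a difference of one to three cells in 100.

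mCR is the exposed row of Table 8. PR needs "marrow blasts >5% but were reduced by 50% or more", so its baseline must exceed 10%. CR needs blood-count thresholds. Hematologic improvement needs absolute changes and abnormal baseline counts. The protocol restricts by baseline elsewhere too: transfusion independence is confined to subjects dependent at baseline (Section 11.7.2), and leukemia-free survival has a rule for baseline blasts of 20% or more (Section 11.7.3).

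At stake is the meaning of the mCR rate. Response rate is a named secondary objective, and Section 4.2 treats efficacy data as part of what the marketing application needs. Without a baseline condition, the rate can include low-blast subjects whose count fell by chance.

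**Working it through.** The plan states no figure for mCR, so there is none to reproduce. The check has two parts.

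**1. Does the rule as written accept a low baseline?** Take a baseline of 4/100 and later marrows of 2/100.
- Final value: 2% ≤ 5%, met.
- Fall: (4 − 2)/4 = 50%, met.
- Duration: met if 2% holds for 4 weeks.
- Counts: not required.
- Eligibility: no blast minimum, so the subject can be enrolled.

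The subject scores as mCR. The two counts cannot be told apart statistically: the exact 95% intervals are 1.1% to 9.9% for 4/100 and 0.2% to 7.0% for 2/100, with Fisher p = 0.68.

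**2. How often would counting error alone do this?**

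Inputs from the protocol: a minimum of 100 cells (Table 9 footnote), and follow-up marrows at Cycles 3, 5 and 7. With 28-day cycles these are 2 × 28 = 56 days apart, so two consecutive scheduled marrows span more than 4 weeks.

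Assumptions: the true blast percentage p does not change; counts are independent binomials on n cells; the observed baseline is above 0 and at most 5%; and the 4-week condition is read as two consecutive qualifying marrows among the three.

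For baseline count x, one later marrow qualifies with probability q(x) = P(X ≤ x/2), X ~ Bin(n, p). Two consecutive of three qualify with probability c(x) = 2q² − q³. Average c(x) over x, using binomial weights rescaled to the allowed baseline range.

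Worked case, n = 100 and p = 3%:

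| Baseline x | Weight | q(x) | c(x) | Weight × c |
|---|---|---|---|---|
| 1 | 0.1687 | 0.0476 | 0.0044 | 0.0007 |
| 2 | 0.2583 | 0.1946 | 0.0684 | 0.0177 |
| 3 | 0.2610 | 0.1946 | 0.0684 | 0.0178 |
| 4 | 0.1957 | 0.4198 | 0.2785 | 0.0545 |
| 5 | 0.1162 | 0.4198 | 0.2785 | 0.0324 |
| Sum | | | | 0.1231 |

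The same calculation over p and n gives the chance of a false mCR per low-baseline subject:

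| True blasts | 100 cells | 200 cells | 500 cells |
|---|---|---|---|
| 4% | 5.1% | 1.4% | under 0.1% |
| 3% | 12.3% | 5.2% | 0.7% |
| 2% | 23.9% | 11.7% | 2.6% |

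**3. What would a floor leave behind?** With 100 cells and two consecutive of three marrows, count all subjects with a given true value, not only those with a low observed baseline. A floor at 5% removes chance responses in 3.9% (true 4%), 10.7% (3%) and 20.3% (2%) of them. Chance responses that start from an observed baseline above 5% remain in 7.5%, 4.8% and 1.3%.

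**The case against.** **The wording may already imply the floor.** A reduction to 5% or below most naturally describes crossing from above that level. This is a fair reading and may be the intent. But the row does not say so, and anyone applying its stated conditions would accept 4% to 2%. If the floor is intended, the change only makes it explicit.

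**The MDS/CMML SAP may deal with it.** The AML SAP has detailed programming and adjudication rules, including one for low screening blasts (its Section 8.1, Appendix D, item 6). The MDS/CMML SAP may have a counterpart. That cannot be checked here, so this point is about the protocol's stated rule and not about how responses were in fact programmed.

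**The duration condition filters chance falls.** It does. A reader might infer that any single halved marrow counts. On that reading, the chance of at least one qualifying marrow in three would be 36.5%, 52.2% and 67.4% at true blasts of 4%, 3% and 2% with 100 cells. The documents do not support this, because the row requires 4 weeks. They do not say whether a second marrow must show it; the table above assumes that it must.

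**100 cells is a minimum.** This also stands. More cells shrink the error quickly, so the 100-cell column is the upper end.

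**mCR is descriptive and secondary.** True. Section 11.7 analyses efficacy as one group, with no comparison between treatments.

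**Conclusion.** The point holds as a gap in a response definition. The protocol admits subjects with marrow blasts of 5% or less, its mCR rule can score them as responders, and the rate is taken over everyone in the Efficacy Analysis Set.

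Under pure counting error and two consecutive qualifying marrows, the chance of a false mCR per low-baseline subject is about 5% to 24% at 100 cells and about 1% to 12% at 200 cells, for true blasts from 4% down to 2%. This rests on independent binomial counts and no true change. A real fall under treatment would add further low-baseline mCRs, which would still not represent clearance of excess blasts.

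The documents do not give the share of enrolled subjects with baseline blasts of 5% or less, so neither a number of false responders nor the inflation of the overall mCR rate can be stated. Nor does anything here bear on the AUC equivalence test or its sample size of 118.

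**What to change.** In the mCR row of Table 8, add that the response applies to subjects with baseline marrow blasts above 5%. In the Section 11.7.1 rate, subjects with a baseline of 5% or less then stay in the denominator but cannot count as mCR. Reporting mCR also within the subset above 5% is optional. Check the separate MDS/CMML SAP, and align it if it does not already contain the condition.

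The cost is one phrase. The screening marrow is already collected, so no new data, visits or subjects are needed. There are two downsides. The all-subject mCR rate may be lower. Some counting error also remains for subjects whose observed baseline falls just above 5%; at a true value of 4% that remainder (7.5%) is larger than what the floor removes (3.9%). The floor's main purpose is to stop subjects with no observed excess blasts from being called marrow responders.

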### Hematological Improvement (HI): lasts at least 8 weeks

Erythroid Response (HI-E): Major Response: Hemoglobin increase ≥1.5 g/dL in the absence of RBC

transfusions.

Platelet Response (HI-P): Major Response: Absolute increase of platelet count from <20 to >20 X 10^9/L and

by at least 100%, or if more than  $20 \times 10^9$ /L, by an absolute increase of at least  $30 \times 10^9$ /L in the absence of platelet

transfusions.

Neutrophil Response (HI-N): Major Response: granulocyte increase ≥100%, and by an absolute increase ≥0.5 x

 $10^{9}/L$ .

a Abnormal baseline counts should be assessed within one week prior to therapy, not influenced by transfusions (no transfusion for at least 1 week).

### 9.3 Pharmacodynamic Assessments

Pharmacodynamic assessments will be based on %LINE-1 demethylation in blood, which will be measured at the following time points:

- Predose on Day 1 of Cycles 1, 2, and 3.
- Days 8, 15, 22 of Cycles 1 and 2.

### 9.4 Safety Assessments

Safety will be assessed by subject reported and investigator observed AEs, along with physical examination, clinical laboratory tests (hematology, chemistry, urinalysis), ECOG performance status, and electrocardiogram (ECG). Time-matched PK assessments for QTc will be performed at specified time points on Day 3 of Cycles 1 and 2, as described in Table 6.

# 9.5 Study Procedures

The procedures to be performed in this study are described in detail in this section.

# 9.5.1 Schedule of Events

Table 9 presents the complete schedule of events for this study, with details following in text. Additional information on the study procedures is provided in the Study Procedures Manual.

Clinical and diagnostic laboratory evaluations are detailed throughout the study. The purpose of obtaining these detailed measurements is to ensure adequate assessments of safety and tolerability. Clinical evaluations and laboratory studies may be performed more frequently if clinically indicated.

Note any deviation from protocol procedures. Investigators are responsible for implementing appropriate measures to prevent the recurrence of violations and deviations and to report to their Institutional Review Board / Independent Ethics Committee (IRB/IEC) according to policy.

**Table 9:** Schedule of Events

| Cyc  | le (28 Days) |     |   |   | 1 |   |              |     |   |   | 2 |   |              |     |   |   | ≥3 |   |    |                 |               |
|--|--------------|-----|---|---|---|---|--------------|-----|---|---|---|---|--------------|-----|---|---|----|---|----|-----------------|---------------|
|  | Cycle Day    |     | 2 | 3 | 4 | 5 | 8, 15,
22 | 1   | 2 | 3 | 4 | 5 | 8, 15,
22 | 1   | 2 | 3 | 4  | 5 | 15 | Trtmt
Disc.a | 30-Day
F/U |
| Study treatment administration (Table 5)                       |              | ×   | × | × | × | × |              | ×   | × | × | × | × |              | ×   | × | × | ×  | × |    |                 |               |
| Procedures   | Screening    |     |   |   |   |   |              |     |   |   |   |   |              |     |   |   |    |   |    |                 |               |
| Informed consent; IPSS risk category, eligibility confirmation | ×            |     |   |   |   |   |              |     |   |   |   |   |              |     |   |   |    |   |    |                 |               |
| Medical history  | ×            |     |   |   |   |   |              |     |   |   |   |   |              |     |   |   |    |   |    |                 |               |
| Randomization  | ×            |     |   |   |   |   |              |     |   |   |   |   |              |     |   |   |    |   |    |                 |               |
| Physical exam/(symptom-directed PE) b               | ×            | (×) |   |   |   |   |              | (×) |   |   |   |   |              | (×) |   |   |    |   |    | ×               | (×)           |
| Height   | ×            |     |   |   |   |   |              |     |   |   |   |   |              |     |   |   |    |   |    |                 |               |
| Weight / BSA calculation c                          | ×            | ×   |   |   |   |   |              | ×   |   |   |   |   |              | ×   |   |   |    |   |    |                 |               |
| Vital signs d                                       | ×            | ×   | × | × | × | × | ×            | ×   | × | × | × | × | ×            | ×   |   |   |    |   |    | ×               |               |
| ECOG status e                                       | ×            |     |   |   |   |   |              | ×   |   |   |   |   |              | ×   |   |   |    |   |    | ×               | ×             |
| 12-lead ECG f                                       | ×            |     |   | × |   |   |              |     |   | × |   |   |              |     |   |   |    |   |    |                 |               |
| ECHO or MUGA g                                      | ×            |     |   |   |   |   |              |     |   |   |   |   |              |     |   |   |    |   |    |                 |               |
| Concomitant treatments/adverse eventsh                         | ×            | ×   | × | × | × | × | ×            | ×   | × | × | × | × | ×            | ×   |   |   |    |   |    | ×               | ×             |
| Transfusion requirements i                          | ×            | ×   |   |   |   |   |              | ×   |   |   |   |   |              | ×   |   |   |    |   |    | ×               | ×             |
| Pharmacokinetics assessments (Table 6 and Table 7)             |              |     |   |   |   |   |              |     |   |   |   |   |              |     |   |   |    |   |    |                 |               |
| Laboratory Assessments   |              |     |   |   |   |   |              |     |   |   |   |   |              |     |   |   |    |   |    |                 |               |
| Hematology j  | ×            | (×) |   |   |   |   | ×            | ×   |   |   |   |   | ×            | ×   |   |   |    |   | ×  | ×               |               |
| Chemistry k   | ×            |     |   |   |   |   |              | ×   |   |   |   |   |              | ×   |   |   |    |   |    | ×               |               |
| Urinalysis   | ×            |     |   |   |   |   |              | ×   |   |   |   |   |              | ×   |   |   |    |   |    | ×               |               |
| Serum or urine pregnancy test m                     | ×            |     |   |   |   |   |              |     |   |   |   |   |              |     |   |   |    |   |    | ×               |               |
| %LINE-1 demethylation (blood) n                     |              | ×   |   |   |   |   | ×            | ×   |   |   |   |   | ×            | ×n  |   |   |    |   |    |                 |               |
| Bone marrow aspirate/biopsy o                       | ×            |     |   |   |   |   |              |     |   |   |   |   |              | ×   |   |   |    |   |    |                 |               |

